6.14.2.1. Common Adverse Events

The percentages of patients with TEAEs will be summarized by treatment using MedDRA Preferred Term nested within System Organ Class for the common TEAEs (occurred in $\geq 10\%$ before rounding of treated patients). Events will be ordered by decreasing frequency within System Organ Class.

The percentages of patients with TEAEs by maximum severity will be summarized by treatment using MedDRA Preferred Term nested within System Organ Class for TEAEs. For each subject and TEAE, the maximum severity for the MedDRA level being displayed (Preferred Term, High Level Term, or System Organ Class) is the maximum post-baseline severity observed from all associated LLTs mapping to that MedDRA level. These summary tables will additionally be provided for the Induction, Maintenance and Extension Periods.

In the event differential dropout rates are seen or to further investigate events of interest, summary tables comparing exposure-adjusted incidence rate (that is, person-time-adjusted incidence rates) over the entire time period will be generated for the Induction and Maintenance Periods.

6.14.2.2. Hypersensitivity Reactions

Two main analyses are performed in support of assessment of potential immediate hypersensitivity, including anaphylaxis and infusion related reactions (IRR), and well as potential non-immediate hypersensitivity.

Time Period A, of potential immediate hypersensitivity, includes all TEAE occurring on the day of study drug administration.

Time Period B, of potential non-immediate hypersensitivity, includes all TEAE occurring strictly after the day of study drug administration (but prior to subsequent drug administration).

Analyses of both time periods use the current standard Medical Dictionary for Regulatory Activities (MedDRA) Standardised Medical Queries (SMQs) to search for relevant events. TEAE are characterized as follows:

- Anaphylactic reaction SMQ (20000021; narrow, algorithm per MSSO SMQ guide, and broad)

- Hypersensitivity SMQ (20000214; narrow and broad)
- Angioedema SMQ (20000024; narrow and broad)
- Preferred term (PT) of Infusion related reaction (10051792)

The number and percentage of patients who experienced a TEAE for the following will be analyzed for each of the two time periods:

- Any narrow or algorithmic term from any one of the 3 SMQs indicated above (that is, combined search across narrow and algorithmic portions of all 3 SMQs)
- Any narrow scope term within each SMQ, separately (that is, narrow SMQ search)
- Any term within each SMQ, separately (that is, broad SMQ search)

Within query, individual PTs that satisfy the queries will be summarized. For Infusion related reaction (PT), the individual LLTs will be summarized.

The Anaphylactic reaction SMQ algorithm will be run only for Time Period A. The SMQ defines a category (A, B, C, D) for each SMQ PT. All Narrow terms have category A, and the occurrence of a Narrow term satisfies the algorithm. Additionally, a pair of PTs *from the same drug administration* satisfies the algorithm if the two events are from different categories (*i.e.*, B&C, or B&D, or C&D). Both contributing events must begin within Time Period A. Tables will summarize (the number of patients experiencing) each PT that contributes to such an algorithmic pair, and include such terms in the combined narrow and algorithmic search. Broad events that do not contribute to the algorithm will be summarized in a distinct portion of the table.

For Time Period A only, the number and percentage of each PT that is not in any of the 3 SMQs will be summarized overall and by individual PT. Only PTs that occur in at least 3 patients receiving LY3074828 will be displayed in this portion of the table.

The PT and LLT are listed for summary in decreasing order of incidence for LY-treated patients. Note that an individual patient may contribute multiple events. Also, a single event may satisfy multiple SMQ, in which case the event contributes to every applicable SMQ.

The analyses of this section will be performed for Induction Period, for Induction and Maintenance Periods combined, and for Induction and Extension Periods combined.

6.14.2.3. Analysis of Injection Site Reactions

A summary will be provided, by treatment group, of the number of patients with reported events that map to any one of the following:

- MedDRA High Level Term (HLT) of Injection site reaction
- HLT of Administration site reaction
- HLT of Infusion site reaction.

The number and percentage of patients who experienced a TEAE for the following will be analyzed:

- Any term from either of the HLTs indicated above (that is, a combined query of these HLTs)
- Any term within each HLT separately

Within HLT, individual PTs that satisfy the queries will be summarized.

The PT will be listed for summary with each category in decreasing order of incidence for LY-treated patients.

The analyses of this section will be performed for Induction Period, for Induction and Maintenance Periods combined, and for Induction and Extension Periods combined.

6.14.3. Deaths, Serious Adverse Events, and Other Significant Adverse Events

The number and percentage of patients who experienced a serious adverse event during the treatment period will be summarized by treatment using MedDRA Preferred Term nested within System Organ Class. Events will be ordered by decreasing frequency within System Organ Class.

These summary tables will be generated for the study overall and additionally will be generated for the Induction, Maintenance and Extension Periods.

In the event differential dropout rates are seen, summary tables comparing exposure-adjusted incidence rate (that is, person-time-adjusted incidence rates) over the entire time period will be generated for the Induction and Maintenance Periods for applicable safety evaluations of interest.

The number and percentage of subjects who permanently discontinued from study treatment due to an adverse event (including adverse events that led to death) during the treatment period will be summarized by treatment using MedDRA Preferred Term nested within System Organ Class. Events will be ordered by decreasing frequency within System Organ Class.

A listing of deaths will be provided. All deaths will be included, regardless of the Investigator's or the Sponsor's judgment about causality, including (1) any deaths occurring during participation of the study, (2) any deaths occurring after a patient leaves (i.e., discontinued from the study or completes the study) if the death is the result of a process initiated during the study, regardless of when it actually occurs. Each listing will include investigator ID, patient ID, treatment group, baseline age, sex, associated AE, whether or not the death and Lilly's assessment of whether the process leading to death (NOT the death itself) began:

- "On study": during study or within the 24-hour day after day of last dose in study.
- "Shortly after study": from the end of the "On Study" time period to 4 weeks after last dose in study or
- "Long after study": more than 4 weeks (or longer, as specified in "Shortly After Study") after the last dose in study

6.14.4. Clinical Laboratory Evaluation

Laboratory evaluations will be summarized and analyzed for the following periods:

- Induction Period,
- Maintenance Period,
- Extension Period (including Extension Induction and Extension Maintenance)

Laboratory tests include all planned analytes as defined in the protocol, excluding those collected in a reflex manner (only collected under certain circumstances).

Values at each visit (starting at randomization) and change from baseline to each visit for laboratory tests will be displayed in box plots (notched box for each treatment with outliers displayed) for patients who have both a baseline and a result for the specified visit. Individual measurements outside of reference limits (defined by the performing laboratory) will also be displayed using distinct symbols overlaying the box plot. Baseline will be the last non-missing observation in the screening period. Original-scale data will be used for the display. Unplanned measurements will be excluded. Displays using both SI and U.S. conventional units will be provided (when different). The following summary statistics will be included in a table below the box plot: N, mean, standard deviation, minimum, Q1, median, Q3, and maximum. Box plots will be used to evaluate trends over time and to assess a potential impact of outliers on central tendency summaries.

Change from baseline to last observation will also be summarized within the box plot of changes (rightmost column) for patients who have both baseline and at least one post-baseline result. Baseline will be the last non-missing observation in the screening period. The last non-missing observation in the treatment period will be used as the last observation. Original-scale data will be used. Unplanned measurements will be excluded. A p-value will be included in the summary statistics at the bottom of the box plot for this assessment, using an ANCOVA model containing terms for treatment and the continuous covariate of baseline measurement.

For quantitative laboratory analyte measurements, 3-panel displays that include a scatterplot, a shift table, and a shift to high/low table will be created. Specifically, for each measurement, both a 3-panel display assessing low values and a 3-panel display assessing high values will be created.

In the 3-panel display to assess low values, the scatterplot will plot the minimum value during the screening period versus the minimum value during the treatment period. Lines indicating the reference limits are included. In cases where limits vary across demographic characteristics, lines indicating the most common limit will be displayed. The shift table will include the number and percentage of patients within each baseline category (minimum value is low, normal, high, or missing) versus each treatment category (minimum value is low, normal, or high) by treatment. Patients with at least one result in the treatment period will be included in the shift table. The shift from normal/high to low table will include the number and percentage of patients by treatment whose minimum baseline result is normal or high and whose minimum treatment result

is low. Patients whose minimum baseline result is normal or high and have at least one result during the treatment period are included. The Fisher's exact test will be used to compare percentages of patients who shift from normal/high to low between treatments.

The 3-panel display to assess high values will be created similarly. The scatterplot will plot the maximum value during the screening period versus the maximum value during the treatment period. The shift table will include the number and percentage of patients within each baseline category (maximum value is low, normal, high, or missing) versus each treatment category (maximum value is low, normal, or high) by treatment. The shift from normal/high to low table will include the number and percentage of patients by treatment whose maximum baseline result is normal or low and whose maximum treatment result is high. Patients whose maximum baseline result is normal or low and have at least one result during the treatment period are included.

For laboratory analyte measurements collected qualitatively, a listing of abnormal findings will be created. The listing will include patient ID, treatment group, laboratory collection date, analyte name, and analyte finding.

6.14.4.1. Hepatic Laboratory Examinations

Analyses for laboratory analyte measurements are described in Section 5.3. This section describes additional analyses for the topic.

To further evaluate potential hepatotoxicity, an eDISH (Evaluation of Drug-Induced Serious Hepatotoxicity) plot will be created. Each subject with at least one post-baseline ALT and total bilirubin contributes one point to the plot. The maximum ALT measurement and the maximum total bilirubin measurement during the treatment period are used. The measurements do not need to be taken at the same blood draw.

The percentages of subjects with the following elevations in hepatic laboratory tests at any time will be summarized between treatment groups:

- The percentages of patients with a alanine aminotransferase (ALT) measurement greater than or equal to 3 times (3X), 5 times (5X), and 10 times (10X) the performing laboratory upper limit of normal (ULN) during the treatment period will be summarized for all patients with a post-baseline value and for subsets based on various levels of baseline value.
 - The analysis of 3X ULN will contain 4 subsets:
 - patients whose non-missing maximum baseline value is less than or equal to 1X ULN,
 - patients whose maximum baseline is greater than 1X ULN but less than 3X ULN,
 - patients whose maximum baseline value is greater than or equal 3X ULN, and
 - patients whose baseline values are missing.

- The analysis of 5X ULN will contain 5 subsets:
 - patients whose non-missing maximum baseline value is less than or equal to 1X ULN,
 - patients whose maximum baseline is greater than 1X ULN but less than 3X ULN,
 - patients whose maximum baseline is greater than or equal to 3X ULN but less than 5X ULN,
 - patients whose maximum baseline value is greater than or equal to 5X ULN, and
 - patients whose baseline values are missing.
- The analysis of 10X ULN will contain 6 subsets:
 - patients whose non-missing maximum baseline value is less than or equal to 1X ULN,
 - patients whose maximum baseline is greater than 1X ULN but less than 3X ULN,
 - patients whose maximum baseline is greater than or equal to 3X ULN but less than 5X ULN,
 - patients whose maximum baseline is greater than or equal to 5X ULN but less than 10X ULN,
 - patients whose maximum baseline value is greater than or equal to 10X ULN, and
 - patients whose baseline values are missing.
- The percentages of patients with an aspartate transaminase (AST) measurement greater than or equal to 3 times (3X), 5 times (5X), and 10 times (10X) the performing laboratory ULN during the treatment period will be summarized for all patients with a post-baseline value and for subsets based on various levels of baseline, as described above for ALT.
- The percentages of patients with a total bilirubin measurement greater than or equal to 2 times (2X) the performing laboratory ULN during the treatment period will be summarized for all patients with a post-baseline value, and subset into 4 subsets:
 - patients whose non-missing maximum baseline value is less than or equal to 1X ULN,
 - patients whose maximum baseline is greater than 1X ULN but less than 2X ULN,
 - patients whose maximum baseline value is greater than or equal to 2X ULN, and
 - patients whose baseline values are missing.

Maximum baseline will be the maximum non-missing observation in the screening period. The maximum value will be the maximum non-missing value from the treatment period. Planned and unplanned measurements will be included.

In addition, the percentages of subjects with treatment-emergent potentially drug-related hepatic disorders will be summarized by treatment by using the MedDRA preferred terms contained in any of the following SMQs:

- Broad and narrow terms in the Liver related investigations, signs and symptoms SMQ (20000008)
- Broad and narrow terms in the Cholestasis and jaundice of hepatic origin SMQ (20000009)
- Broad and narrow terms in the Hepatitis non-infections SMQ (20000010)
- Broad and narrow terms in the Hepatic failure, fibrosis and cirrhosis and other liver damage SMQ (20000013)
- Narrow terms in the Liver-related coagulation and bleeding disturbances SMQ (20000015)

The percentage of subjects with any one of the terms will be summarized in addition to the percentages for each MedDRA preferred term. The percentages of subjects with potentially drug-related hepatic disorders that led to permanent study treatment discontinuation will be summarized similarly.

These analyses will be provided for the Induction and Maintenance Periods. Only the summary of ALT (3X, 5X, and 10X), AST (3X, 5X, and 10X), and total bilirubin (2X) at any time will be provided for the Extension period.

Individual graphical patient profiles will be prepared for subjects with an ALT or AST measurement greater than or equal to 5X ULN or with an alkaline phosphatase measurement greater than or equal to 2X ULN. A graphical patient profile will be created for any patient meeting the criteria from the safety population (any phase, any medication). The graphical patient profile will include demographics, disposition, and a display of study drug exposure, adverse events, medications, and the liver-related measurements over time. The review for these subjects includes an assessment of the proximity of any ALT or AST elevation to any total bilirubin elevation, alkaline phosphatase levels, gamma-glutamyl transpeptidase (GGT) levels, other potential causes, and the temporal association with events such as nausea, vomiting, anorexia, abdominal pain, or fatigue.

A plot of maximum post-baseline ALT vs. maximum post-baseline total bilirubin will be created that includes all patients from the safety population. Each subject with at least one post-baseline ALT and total bilirubin contributes one point to the plot. The maximum ALT measurement divided by upper limit of normal (ULN) and the maximum total bilirubin measurement divided by ULN during the treatment period are used. The measurements do not need to be taken at the

same blood draw. Symbols will be used to indicate treatments (concatenated when multiple treatments are taken).

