8.3.2. Discontinuation of Investigational Product

Discontinuation of the investigational product for abnormal liver test results should be considered by the investigator in consultation with the Lilly-designated medical monitor when a subject meets any of the following conditions:

- ALT or AST level $>8\times$ ULN
- ALT or AST level $>5\times$ ULN for more than 2 weeks
- ALT or AST level $>3\times$ ULN and total bilirubin level $>2\times$ ULN or prothrombin time $>1.5\times$ ULN

- ALT or AST level $>3\times$ ULN with the appearance of fatigue, nausea, vomiting, right-upper-quadrant pain or tenderness, fever, rash, and/or eosinophilia ($>5\%$)

Subjects who discontinue the investigational product early will have early termination procedures performed as shown in the study schedule ([Attachment 1](#)).

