Attachment 4. Protocol I6T-MC-AMAC Hepatic Monitoring Tests for Treatment-Emergent Abnormality

Selected tests from the list below may be obtained in the event of a treatment-emergent hepatic abnormality per judgment of the investigator and may be required for subject follow-up as determined after consultation with the Lilly clinical research physician or designee.

Hepatic Monitoring Tests

Hematology^a

Hemoglobin
Hematocrit
RBC
WBC
Neutrophils, segmented
Lymphocytes
Monocytes
Eosinophils
Basophils
Platelets

Chemistry^a

Total bilirubin
Direct bilirubin
Alkaline phosphatase
ALT
AST
Total protein
GGT
Albumin

Hepatic Coagulation^a

Partial prothrombin time
Prothrombin time, INR

Other Labs^{a,b}

Hepatitis A antibody, total
Hepatitis A antibody, IgM
Hepatitis B surface antigen
Hepatitis B surface antibody
Hepatitis B Core antibody
Hepatitis C antibody
Hepatitis E antibody, IgG
Hepatitis E antibody, IgM
Haptoglobin^a
LDH
Antinuclear antibody^a
Alkaline phosphatase isoenzymes
Anti-smooth muscle antibody^a
CPK

Abbreviations: ALT = alanine aminotransferase; AST = aspartate aminotransferase; CPK = creatinine phosphokinase; GGT = γ -glutamyl transferase; IgG = immunoglobulin G; IgM = immunoglobulin M; INR = international normalized ratio; labs = laboratory tests; LDH = lactate dehydrogenase; RBC = red blood cells; WBC = white blood cells.

^a Assayed by Lilly-designated or local laboratory.

^b Reflex/confirmation dependent on regulatory requirements and/or testing availability.

Attachment 5. Protocol I6T-MC-AMAC Mayo Scoring System for the Assessment of Ulcerative Colitis Activity

Stool Frequency	Score
Normal number of stools for subject	0
1 to 2 stools more than normal	1
3 to 4 stools more than normal	2
5 or more stools than normal	3
Rectal Bleeding	Score
No blood seen	0
Streaks of blood with stool less than half of the time	1
Obvious blood with stool most of the time	2
Blood alone passed	3
Endoscopic Findings	Score
Normal or inactive disease	0
Mild disease (erythema, decreased vascular pattern)	1
Moderate disease (marked erythema, absent vascular pattern, friability, erosions)	2
Severe disease (spontaneous bleeding, ulceration)	3
Physician's Global Assessment	Score
Normal	0
Mild disease	1
Moderate disease	2
Severe disease	3
Mayo Score = Stool Frequency + Rectal Bleeding + Endoscopic Findings + Physician's Global Assessment	

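### The SAP's liver-profile rule skips patients with ALT or AST >3x to <5x ULN, bilirubin >2x ULN and ALP <2x ULN, and no table counts the transaminase-bilirubin combination

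*SAP*

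**What the plan says.** **Profiles.** SAP 6.14.4.1: "Individual graphical patient profiles will be prepared for subjects with an ALT or AST measurement greater than or equal to 5X ULN". The only alternative trigger is ALP at or above 2x ULN. The rule applies to the safety population in any phase. Each profile plots the liver tests over time next to exposure, adverse events and medications. "The review for these subjects includes an assessment of the proximity of any ALT or AST elevation to any total bilirubin elevation".

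**Tables.** The same section tabulates ALT (3x, 5x, 10x ULN), AST (3x, 5x, 10x ULN) and total bilirubin (2x ULN). Each is subset only by its own baseline level.

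**Joint plots.** There are two. For the eDISH plot, "The maximum ALT measurement and the maximum total bilirubin measurement during the treatment period are used". Then, for the whole safety population, "A plot of maximum post-baseline ALT vs. maximum post-baseline total bilirubin will be created". In both, the two maxima may come from different blood draws.

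**Periods.** "These analyses will be provided for the Induction and Maintenance Periods"; for the Extension, this part of the section keeps only the single-test threshold summaries.

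**Protocol.** Section 8.3.2 lists conditions under which stopping study drug should be considered. One is ALT or AST above 3x ULN together with "total bilirubin level $>2\times$ ULN or prothrombin time" above 1.5x ULN.

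**The concern.** The profile review exists to judge whether transaminase and bilirubin rises belong together, but patients are selected for it without regard to bilirubin. An isolated ALP of 2x ULN earns a profile; ALT of 4x ULN with bilirubin of 4x ULN and a normal ALP does not. The protocol itself treats the second pattern as a reason to consider stopping drug.

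Two things are at stake. A patient in the gap misses the structured timing review that other liver cases receive. And the report cannot state from its planned tables how many patients per arm had the combination, not even that the number was zero.

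**Working it through.** The plan states no figure on this point, so the check is of the rules themselves, followed by an illustration of scale.

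**1. The rules (values in multiples of ULN)**

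- Protocol 8.3.2, bilirubin limb: (ALT >3 or AST >3) and bilirubin >2.
- SAP 6.14.4.1, profile: ALT >=5 or AST >=5 or ALP >=2.
- Meets the first but not the second: ALT and AST both <5, at least one of them >3, bilirubin >2, ALP <2.

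Example patients:

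| ALT | AST | Bilirubin | ALP | Meets 8.3.2 limb | Profile | Position on the ALT-bilirubin plots |
|---|---|---|---|---|---|---|
| 4 | 1 | 4 | 1 | yes | no | high ALT, high bilirubin |
| 1 | 4 | 4 | 1 | yes | no | normal ALT, high bilirubin; AST not shown |
| 1 | 5 | 4 | 1 | yes | yes | normal ALT, high bilirubin; AST shown in the profile |
| 1 | 1 | 1 | 2 | no | yes | normal on both |

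**2. Grid check**

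ALT and AST each took the values 1, 2.9, 3, 3.1, 4, 4.9, 5 and 8; bilirubin 1, 2, 2.1 and 4; ALP 1, 1.9, 2 and 3.

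- ALT-AST pairs with both <5: 6 x 6 = 36. Pairs with neither >3: 3 x 3 = 9. That leaves 27.
- Bilirubin >2: 2 values. ALP <2: 2 values.
- Patterns that meet the limb but get no profile: 27 x 2 x 2 = 108. The largest ALT, AST and ALP among them are 4.9, 4.9 and 1.9, so the gap is exactly the set named in step 1.
- Of these, ALT >=3: (3 x 6 + 1 x 3) x 4 = 84. They fall in the high-ALT, high-bilirubin region of the plots.
- ALT <3, so AST-driven: (2 x 3) x 4 = 24. They fall outside that region.

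These counts show the logic only; they are not patient frequencies.

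**3. Count of displays in SAP 6.14.4.1**

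There are two joint ALT-bilirubin plots, no AST-bilirubin plot, three single-test threshold analyses, and no table of the combination. Separate percentages for AST and bilirubin cannot show whether the same patient had both.

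**4. Illustration of scale**

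The documents give no rate. Assume a true rate p of 0.1% to 0.5% for the whole unprofiled pattern, ALT-driven and AST-driven together, with n = 240. The expected number is np, and the chance of at least one is 1 - (1 - p)^n.

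- p = 0.001: 240 x 0.001 = 0.24 expected; 1 - 0.999^240 = 0.213.
- p = 0.005: 240 x 0.005 = 1.2 expected; 1 - 0.995^240 = 0.700.

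**The case against.** The best counter-argument is that such a patient is hard to miss altogether. ALT-driven cases are points on the plots, marked by treatment. An AST-driven patient still stands out on bilirubin and is counted in the AST and bilirubin tables. With so few expected, looking up AST for the bilirubin outliers is quick. Clinically significant findings should be reported (Protocol 10.3.1), and deaths, SAEs and AEs leading to drug discontinuation get narratives (SAP 6.14.2). SAP 6.1 allows further exploratory analyses, and the revision history says the hepatic summaries were aligned with current standards, so the cut-offs look deliberate. All of this stands, and it keeps the point minor. But none of these routes gives a combined count or guarantees a timing review. A narrative depends on how the case was reported, because Protocol 8.3.2 only asks that stopping be considered.

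Four stronger readings are tempting, and the documents do not support them:

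- *No AST-driven case appears in any joint display.* A patient with AST >=5x ULN or ALP >=2x ULN gets a profile showing the liver tests together. The statement is true only of AST >3x to <5x with ALT <3x and ALP <2x ULN.
- *Follow-up liver tests drop out of the analysis.* SAP 6.14.4 does say "Laboratory tests include all planned analytes as defined in the protocol, excluding those collected in a reflex manner", and Protocol Attachment 4 tests are done on occurrence. But SAP 6.14.4.1 includes unplanned as well as planned measurements, and ALT, AST, ALP and bilirubin are planned analytes. For the other Attachment 4 tests, nothing says that a profile would show them.
- *The Extension, with its planned 1000 mg IV induction dose, is uncovered.* The hepatic SMQ tables are not provided there, but AE, severity and SAE tables and the single-test thresholds are, and profiles apply in every phase.
- *The SAP breaches the protocol, or patients are less safe.* Protocol 8.3.2 sets no reporting rule, and Protocol 10.3.3 has the investigator start monitoring at ALT or AST above 3x ULN or bilirubin above 2x ULN.

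**Conclusion.** The gap is real and minor. It rests on the wording of SAP 6.14.4.1 set against the bilirubin limb of Protocol 8.3.2; the prothrombin-time limb and the other stopping conditions are not part of it. Within the unprofiled group, ALT-driven cases lose the profile and the timing review but remain visible by treatment. AST-driven cases also lose any display of the AST rise against bilirubin. They surface otherwise only through single-test tables, AE or SAE reporting, narratives or raw listings.

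Few or no patients are expected. The 21% to 70% chance of at least one rests on an assumed rate for the whole unprofiled pattern. It should not be read as the chance of a hidden case, since the ALT-driven part of that pattern is on the plots. No figure can be given for the AST-driven part alone.

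**What to change.** In SAP 6.14.4.1:

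1. Add to the profile trigger, for all phases: ALT or AST >=3x ULN and total bilirubin >=2x ULN. Using >= matches the SAP's own cut-offs and captures every case under the protocol's > limits.
2. Add one table row, by treatment and by period (Induction, Maintenance, Extension), counting patients who meet this criterion.
3. Add a short listing of those patients with ALT, AST, total bilirubin and ALP values and collection dates, so that rises on the same draw can be identified. No fixed time window is needed.

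The cost is the SAP wording, one derived flag, one row, one listing and possibly a few extra profiles. No new data collection is required.
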